Serum beta-human chorionic gonadotrophin (β-HCG) pregnancy test (i)		>	۲°													(X)
Human immunodeficiency virus (HIV), Hepatitis A, B, and C tests	х															
Haematology (j)	Х	>	۲°				Xd		Х				Х	(X)	Х	X
Biochemistry (j)	х	>	۲°						Х				Х	(X)	Х	Х
Coagulation (j)	Х	>	( °				Xd		Х				Х	(X)		Х
Cardiac enzymes	х	)	۲°						х	1			Х			
Thyroid function test	х	()	<)°									1				
Blood - immune markers (k)	Х	X°	X	х			Xq	х	х	х	Х	Х	Х	х	Х	Х
Blood – transcriptomics markers			BD	х		х	BDq	BD	BD	BD	BD	BD	BD	х		

	Screening		QUARANTINE ISOLATION									Γ	Early				
Study phase >	phase*	Admission to quarantine		Human viral challenge (HVC)					Post	HVC da	iys	Discharge	Clinic visit		withdrawal visit		
Study day →	Day -56 (Day -90 for	Day	Day		Day 0		Day	Day	Day	Day	Day	Day	Day	Day	Follow-up		
Procedure V	influenza serology) to Day -3	-2	-1	Pre	Challenge	Post	1	2	3	4	5	6	7	8	Day 28 (± 3 days)		
Blood – deoxyribonucleic acid (DNA) - genomics		>	۲°														
Blood - Pharmacokinetics (PK)		>	۲°				2X t	Х		Х		Х		Х	Х		Х
Blood - anti-drug antibodies (ADA)		>	۲°				2X t	х		Х		х		х	х		х
Collection of Respiratory Samples																	
Nasopharyngeal swab / nasal wash - Respiratory pathogen screen (I)	т	X°	(X) p														
Nasopharyngeal swab / nasal wash - Rapid viral antigen test or polymerase chain reaction (PCR)														(X) p			(X)
Nasopharyngeal swab / nasal wash – Virology (m) and exploratory research	т		x				BDq	BD	BD	BD	BD	BD	BD	х			х
Nasal sample (nasosorption / mid turbinate swab) – PK and exploratory immunology			х				Xď	x	Х	х	х	х	х	х			
Safety Assessments																	
Adverse events (n)	х		continuous							Х							
Concomitant medications (n)	Х							con	tinuous								Х

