# hvivo

CONFIDENTIAL

а	Study specific consent may occur on the day of admission, providing all required eligibility information has been collected through hVIVO Generic Screening process.
b	Only the applicable Inclusion / Exclusion criteria will be reviewed at each time point.
с	Height will be taken at Screening only.
d	Urine pregnancy tests will be performed in female participants of childbearing potential.
е	Vital signs will be taken at the same time(s) each day (±1 hour). On Day 1 the vital signs will be performed pre-infusion, and at 15 minutes, 30 minutes, 60 minutes, 90 minutes, 2 hours, 4 hours, and 8 hours after the start of the drug infusion.
f	Distribution of paper tissues and bags will start on Day -1, with the first collection on Day 0. Thereafter collection of tissues will occur at the same time points (±1 hour) with tissues distributed 24 hours ahead.
g	Assessments will be performed at the same time points (±1 hour) during quarantine.
h	A serum FSH test will be performed in all post-menopausal female participants.
i	Blood serum pregnancy test (β-hCG) will be performed in all female participants.
j	Blood may be drawn under non-fasted conditions. Repeat bloods may be drawn under fasted conditions if a lipid profile (triglyceride) or glucose is required (at Principal Investigators [PIs] discretion).
k	Blood will be collected for: i) virus serology (influenza antibody assay) to determine eligibility (at screening) and seroconversion (at Day -2 / -1 & Day 28), and ii) exploratory immune markers.
I	Nasopharyngeal swab or nasal wash for respiratory virus screen to assess for the presence of other respiratory viruses; if found positive the participant will not be eligible for the current quarantine.
m	Nasopharyngeal swabs (or nasal wash, if appropriate) will be collected for viral load assessments and exploratory immunology. Post inoculation nasal virology samples will be collected and used for qRT-PCR and viral culture assay.
n	Adverse events and concomitant mediations are reviewed throughout the study including pre- and post-infusion with IMP/placebo and pre- and post-inoculation.
0	Can be performed on Day -2 or Day -1. If admission at Day -1, all procedures scheduled for Day -2 can be performed on Day -1, as appropriate.
р	Optional and may be collected or not as per PI discretion for exploratory research.
q	Pre-infusion (only applicable to the first assessment on Day 1).
r	Post-dose ECG.

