## 4. Study Design

## 4.1. Overall Design

This is an exploratory randomised, Phase 2a, double blind, placebo-controlled study to evaluate the safety and treatment efficacy of SAB-176 against Influenza A/California/2009 H1N1 virus infection in healthy adult participants.

Up to 60 eligible participants will be randomized in a 1:1 ratio to receive either SAB-176 (up to 50 mg/kg dose) or placebo. Healthy adult participants will be pre-screened for serosuitability for Influenza A/California/2009 H1N1 virus challenge. Serosuitable participants who sign the study specific informed consent form (ICF) will be challenged with an intranasal administration of Influenza A/California/2009 H1N1 virus on Day 0. Participants will be given an IV infusion of SAB-176 or placebo on Day 1. Participants will be held in guarantine until Day 8.

The Study Schematic - showing participant progression through the study - is presented in Section 1.1; the Schedule of Activities (SoA) is presented in Section 1.2.

The total duration of study participation for a participant is approximately 5 weeks from signing study specific ICF to the participant's last scheduled visit, with the following sequence and duration of study phases:

- Screening phase: from 56 days (90 days for influenza serology) up to Day -3. Historical pre-screening data collected through the hVIVO Generic Screening process within 56 days (90 days for influenza serology) up to Day -3 may be transferred to this study after the study specific ICF has been signed by the participant.
- Inpatient phase: Participants will be resident in the Quarantine Unit for approximately 11 days (e.g., from admission on Day -2 to planned discharge on Day 8). Procedures will include:
  - Pre-human viral challenge (HVC):
    - Admission to Quarantine Unit on Day -2 / -1.
  - HVC:
    - Inoculation with Challenge virus on Day 0.
  - Post-HVC:
    - $\circ$   $\:$  IV infusion with SAB-176 or placebo on Day 1.
    - Day 1 to 7 onwards and each day study assessments will be conducted as per SoA.
    - Participants will be discharged from the Quarantine Unit on Day 8 (or may remain longer at the Principal Investigator's [PIs] discretion).

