# 9.3. Populations for Analyses

Population	Description
Enrolled	All participants who signed the study specific ICF, their eligibility is confirmed, and have been inoculated with the Challenge virus.
Randomised	All enrolled participants randomly assigned to study intervention.
Intent to Treat (ITT) Analysis Set	All participants randomly assigned to study intervention who received the study intervention (SAB-176 or placebo).
The Intent to Treat Infected (ITT-I)	All participants randomly assigned to study intervention who received the study intervention and were infected with Challenge virus as per the definition of laboratory confirmed infection for this protocol
Per Protocol (PP) Analysis Set (or Evaluable set)	All participants randomly assigned to study intervention who received the study intervention (ITT Analysis Set participants) who have no major protocol deviation likely to impact the efficacy evaluation, and who complete the quarantine period up to the final day of quarantine, (Day 8).

The following populations are defined:

Population	Description
Safety Analysis Set	All participants randomly assigned to study intervention and who received at least one dose of study intervention. Participants will be analysed according to the intervention they actually received.
PK Analysis Set	All participants randomly assigned to study intervention with at least three post-dose PK results.

The primary efficacy analysis will be on the PP Analysis Set. The ITT and ITT-I Analysis Sets will be used for supportive analyses on all or part of the primary and secondary efficacy endpoints, as defined in the Statistical Analysis Plan (SAP). The safety evaluation will be performed on the Safety Analysis Set. Additional analysis sets may be defined in the SAP.

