#### Table 6: Methods for Analysis of Secondary Endpoints

Endpoints	Planned analysis
Peak viral load of VL-AUC of Influenza A/California/2009 H1N1 virus as defined by the maximum viral load determined by quantifiable qRT-PCR measurements in nasal samples starting two days post viral challenge (Day 2) up to discharge from quarantine.	Wilcoxon-rank-sum test (alternative: t-test if underlying assumptions valid)
Duration of influenza quantifiable qRT-PCR measurements in nasal samples.	Wilcoxon-rank-sum test (alternative: t-test if underlying assumptions valid)
Area under the curve over time of total clinical symptoms score (TSS-AUC) as measured by graded symptom scoring system (categorical and visual analogue scales).	t-test if underlying assumptions valid (alternative: Wilcoxon-rank- sum test)
Peak symptoms diary card score: peak total clinical symptoms score (TSS) as measured by graded symptom scoring system (categorical and visual analogue scales).	t-test if underlying assumptions valid (alternative: Wilcoxon-rank- sum test)
Peak daily symptom score: Individual maximum daily sum of symptom score.	t-test if underlying assumptions valid

Endpoints	Planned analysis
	(alternative: Wilcoxon-rank- sum test)
Number (%) of participants with Grade 2 or higher symptoms.	Chi-square test
Incidence of symptomatic infection due to Influenza A/California/2009 H1N1 virus, compared to placebo as measured by: RT-PCR-confirmed symptomatic influenza infection defined as:	Chi-square test (on the composite and each component)

RT-PCR-confirmed influenza infection, AND

Clinical symptoms

	

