# 10.6.2. Study definition of infection and illness

TERM	CRITERIA (RESPIRATORY SYNCYTIAL VIRUS, HEART RATE VARIABILITY AND INFLUENZA STUDIES)			
Seroconversion	A ≥4-fold increase in Virus specific antibodies from baseline to follow-up post-quarantine			
The following definitions should only be applied to data collected from Day 1 onwards				

TERM	CRITERIA (RESPIRATORY SYNCYTIAL VIRUS, HEART RATE VARIABILITY AND INFLUENZA STUDIES)
Lower Respiratory Tract Illness	
 
Any one of the following signs and/or symptoms on two consecutive scheduled assessments, at least one of which must feature Grade 2 severity, or if any of the following attain Grade 3 severity once: 
 
Self-reported symptoms: cough, shortness of breath, chest tightness and wheeze.
 
Physician findings: Abnormal breath sounds externally (e.g., stridor, wheezing) and on chest auscultation (rhonchi, crepitations or other).
 

Upper Respiratory Tract Illness	
 
Any one of the following signs and/or symptoms on two consecutive scheduled assessments, at least one of which must feature Grade 2 severity, or if any of the following attain Grade 3 severity once: 
 
Self-reported symptoms: rhinorrhoea (runny nose), nasal congestion (stuffy nose), sore throat, sneezing.
 
Physician findings: nasal discharge, otitis, pharyngitis, sinus tenderness.
 
 
 

Systemic Illness	Fulfils the criteria for febrile illness, or fulfils the definition of upper respiratory tract illness and/or lower respiratory tract illness and any one of the following symptoms on two consecutive scheduled assessments, at least one of which must feature Grade 2 severity, or if any of the following attain Grade 3 severity once: • malaise • headache • muscles and/or joint ache • chilliness • feverishness.
Febrile Illness	Any occurrence of temperature $\geq$ 37.9°C (confirmed by a repeat measurement as $\geq$ 37.9°C within 20 to 60 minutes).

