Viral shedding	
 
One or both of the following definitions must be met:
 
At least two positive quantifiable detections by viral load qPCR assay specific for the Challenge virus, reported on two or more consecutive days and from two independent samples (which can either be the same type of sample or different e.g., throat swab and nasal wash or two nasal wash samples).
 
One positive detection by viral load qPCR assay, specific for the Challenge virus, in which an aliquot of the same sample has also tested positive in a viral culture assay appropriate for detecting the Challenge virus.
 

Laboratory confirmed Virus infection	Viral shedding definition has been met.

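### Infection and illness endpoints meant to show the effect of a Day 1 infusion can be met by swabs and diary cards taken before it, which can dilute the incidence comparisons by an unknown amount

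*Combined protocol and SAP*

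**What the plan says.** Section 4.1 puts challenge and treatment on successive days: "Inoculation with Challenge virus on Day 0", then the infusion on Day 1. In the Schedule of Activities (section 1.2) the row "Nasopharyngeal swab / nasal wash – Virology (m) and exploratory research" is twice daily on Day 1 and carries note q, which reads "Pre-infusion (only applicable to the first assessment on Day 1"). The symptom diary card, tympanic temperature and directed physical examination carry the same note on Day 1.

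Section 10.6.2 introduces its illness and infection criteria with "The following definitions should only be applied to data collected from Day 1 onwards". Viral shedding can then be met in two ways. The first needs two quantifiable qPCR results on consecutive days from independent samples. The second needs one sample: "One positive detection by viral load qPCR assay, specific for the Challenge virus, in which an aliquot of the same sample has also tested positive" by viral culture. Laboratory-confirmed infection is defined only as "Viral shedding definition has been met", with no added requirement for a second day or for seroconversion. Upper and lower respiratory tract illness are each met if one listed sign or symptom reaches Grade 3 once.

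Several outcomes use these terms. The ITT-I set (section 9.3) takes treated participants who "were infected with Challenge virus as per the definition of laboratory confirmed infection for this protocol". Symptomatic infection confirmed by RT-PCR or by culture is a secondary endpoint (section 3). Table 6 gives the RT-PCR version a chi-square test, both on the composite and on each component. Infection rate and the illness categories are exploratory. By contrast, Table 6 counts qRT-PCR peak viral load only "in nasal samples starting two days post viral challenge (Day 2) up to discharge from quarantine".

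**The concern.** The stated objectives are that SAB-176 reduces symptomatic infection, infection and illness. An event already met before the infusion cannot be prevented by it, yet the Day 1 start lets such events count. A swab taken the day after live virus was placed in the nose might also recover inoculum rather than new virus, and no passage excludes that sample or mentions carry-over.

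The same holds for symptoms. A single Grade 3 entry on the pre-infusion diary card, or a Grade 3 finding at the pre-infusion examination, settles respiratory tract illness for that participant whatever follows. Cases of this kind appear in both arms regardless of treatment, so they move risk ratios towards 1 and reduce the chance of seeing a real effect.

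**Working it through.** **The plan's own figure.** Section 9.2 gives 60 participants for a 60% relative reduction in VL-AUC with an 81% coefficient of variation. With the control mean set to 1 and a common SD of 0.81, n per arm = 2 × [0.81 × (1.96 + 0.8416) / 0.60]² = 28.6, so 29. A t-test calculation gives 29.6, so 30 per arm, with 80.5% power. The figure reproduces, and it does not depend on the infection definition.

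**Windows compared.** All windows below draw on the same participants' Day 1 to Day 8 observations.

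| Item | Starts | Can pre-infusion data count? |
|---|---|---|
| Laboratory-confirmed infection (10.6.2) | Day 1 | Yes; one swab is enough if qPCR and culture positive |
| Upper or lower respiratory tract illness (10.6.2) | Day 1 | Yes; one Grade 3 entry is enough |
| qRT-PCR peak viral load (Table 6) | Day 2 | No |

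Under the two-detection route, Day 1 and Day 2 together also suffice.

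**Size for infection incidence.** Let p be the true infection rate and r the share of never-infected participants who are qPCR and culture positive on Day 1 only.

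- Classified infected = p + (1 − p)r.
- Never-infected share of those classified infected = (1 − p)r / [p + (1 − p)r].
- Inputs: p = 65% on placebo (Table 1, which does not say what definition produced it); p = 40% on SAB-176 (assumed); 30 per arm (section 9.2). The documents give no value for r, so a range is shown.

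| r | Placebo | SAB-176 | Risk ratio | Extra cases per 30 (placebo v SAB-176) | Never-infected share (placebo v SAB-176) |
|---|---|---|---|---|---|
| 0 | 65% | 40% | 0.40/0.65 = 0.62 | 0 v 0 | 0 v 0 |
| 10% | 0.65 + 0.35 × 0.10 = 68.5% | 0.40 + 0.60 × 0.10 = 46% | 0.67 | 1.05 v 1.8 | 5% v 13% |
| 30% | 75.5% | 58% | 0.77 | 3.15 v 5.4 | 14% v 31% |

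The carry-over rate among the never-infected is the same in both arms. The number of extra cases is larger in the arm with fewer true infections.

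With a stronger assumed effect (26% on SAB-176, a 60% reduction from 65%), the risk ratio goes from 0.40 to 0.49 at 10% carry-over and 0.57 at 20%. Power with 30 per arm goes from 88% to 79% and 69%.

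**Size for the composite.** Let s₁ and s₀ be the probabilities of qualifying symptoms in truly infected and never-infected participants, taken as equal across arms. The composite rate is p·s₁ + (1 − p)·r·s₀ = s₁[p + (1 − p)·r·(s₀/s₁)]. The risk ratio is therefore the one tabulated above with r replaced by r × s₀/s₁. As long as never-infected participants are symptomatic less often than infected ones, the composite is diluted less than infection alone. The documents give neither probability.

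**The case against.** The strongest reply is that the definition already guards against carry-over. The single-swab route needs culturable virus, so leftover RNA is not enough, and the other route needs two quantifiable results on consecutive days. At 10% carry-over only about one placebo and two SAB-176 participants are affected. Section 9.1 rests efficacy conclusions on the primary analysis and treats other tests as illustrative. The exploratory endpoints are optional, and section 9.4.6 plans no formal testing of them unless specified. Section 10.6.2 is not expressly cited for the RT-PCR-confirmed secondary endpoint, and the separate SAP and Analytical Plan, which are not in the text reviewed, may set a window. All of this stands as a limit on size and importance. It does not give a reason to let pre-infusion data satisfy an endpoint about the infusion, and Table 6 does test the infection component.

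A reader might infer that ITT-I is contaminated in a way that flatters SAB-176, and that its definition should move to Day 2. The documents do not support this.

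- The unequal shares in the table arise only if SAB-176 truly lowers infection. With equal true rates the shares are equal, so this route does not create an apparent benefit from nothing.
- A participant positive only on Day 1 need not be uninfected. An infection cleared quickly after the infusion would look the same.
- The pre-infusion swab is the only post-challenge virology sample that treatment cannot influence. Without it, ITT-I membership would depend wholly on post-infusion data.

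A reader might also take the two start days as an error in themselves. They are not: a maximum can be dominated by one early value in a way that a dual-assay classification is not, so different windows can be deliberate. What is missing is a stated reason.

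**Conclusion.** The concern holds for the treatment-effect incidence endpoints. As written, a single pre-infusion qPCR- and culture-positive swab can make a participant laboratory-confirmed infected, and one pre-infusion Grade 3 symptom can make a participant a respiratory illness case. Counting these can pull the secondary symptomatic-infection comparison, and the exploratory infection and illness comparisons, towards no difference.

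The size cannot be fixed from the documents. Risk ratios of 0.67 to 0.77 in place of 0.62 rest on an assumed 40% infection rate on SAB-176 and assumed carry-over of 10% to 30%. They apply to infection alone, and dilution of the composite should be smaller because symptoms are also required. Illness dilution was not quantified. The primary VL-AUC analysis is on the per-protocol set, which does not require infection, so neither it nor the sample size is affected. Nothing here shows that never-infected participants will enter ITT-I, only that the definition allows it.

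**What to change.** Before unblinding, state separate windows in Appendix 6 and the SAP for the two uses of the definitions.

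- **Incidence endpoints** (RT-PCR- and culture-confirmed symptomatic infection, infection rate, and upper respiratory, lower respiratory, systemic and febrile illness): count symptoms and illness only from the first post-infusion assessment, and virology from Day 2, in line with the peak viral load window in Table 6. Report the Day 1-onwards version as a sensitivity analysis.
- **ITT-I**: keep the Day 1-onwards definition, and add a supportive ITT-I analysis whose membership uses swabs from Day 2 onwards.

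State the reason for each window and say that RT-PCR-confirmed infection uses the section 10.6.2 definition, if it does. If the SAP or Analytical Plan already sets a window, cite it in Appendix 6.

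The cost is a short text change and one extra table of alternative-window results. A participant positive only on Day 1 would no longer count as an infection event in the main incidence analysis. The second Day 1 swab, which note q does not place before the infusion, would be set aside there too. The sensitivity analysis shows the effect of both choices.
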